#### Vaccination Procedure

- Review criteria for delay or cancellation of vaccination. See Sections 6.3 and 8.1 for an overview of the criteria leading to delay or cancellation of vaccine administration.

In case of delay, the vaccination should take place within the allowed time windows. The reasons for delay or cancellation should be documented in the subject's chart.

- Administer the trial vaccine dose according to the subject's assignment.

#### Post-vaccination Procedures

- Observe the subject on site for at least 30 minutes following vaccination for safety monitoring. At the end of the observation period:
  - Measure vital signs (body temperature, pulse, blood pressure; see Section 9.3.6).
  - The subject may not be discharged until vital signs are within normal range or have returned to pre-vaccination levels.
  - Record the occurrence of any AEs following trial vaccination.
- Instructions for the subject:
  - Instruct the subject how to measure solicited AEs and how to complete the eDiary. The subject should record solicited local and systemic AEs occurring on the day of vaccination and the following 7 days, and unsolicited AEs (i.e., the occurrence of all other AEs) occurring on the day of vaccination and the following 28 days.
  - Remind the subject to call the site immediately to report the following:
    - If he/she experiences any concerning local or systemic reactions or other medical event.
    - Any medically-attended visits that are not routine visits for physical examination or vaccination, such as visits for hospitalization, an emergency room visit, or an otherwise unscheduled visit to or from medical personnel (medical doctor) for any reason.
    - Experience a serious medical event, have a change in overall health or be diagnosed with a new medical condition by a doctor. These should be reported regardless of the perceived relationship between the event and the trial vaccine.
  - Remind the subject to contact the site immediately if he/she has any of the symptoms suggestive of COVID-19. In addition, subjects will be messaged up to twice a week to provide a yes or no response to having COVID-19 symptoms. Those who respond "yes" will be contacted by trial staff for follow-up information, if the investigator considers the symptoms could potentially indicate a COVID-19 case (see Section 9.2.1 and Section 9.5).
  - The subject should also be reminded to contact the site immediately if he/she had a positive SARS-CoV-2 test performed outside of the site, irrespective of whether they were symptomatic (COVID-19 illness) or asymptomatic at the time of the test.

Note: Subjects without symptoms may have been tested for several reasons, for example, close exposure to a known person with SARS-CoV-2 infection or as part of their routine screening as a healthcare provider.

### **9.1.1.2 Phone Call: Day 2 (-0/+0 day)**

The purpose of this phone contact is to inquire about the subject's general well-being and to assess safety 1 day after the first trial vaccination.

- During the phone call:
  - Review and record any newly reported safety data including solicited and unsolicited AEs, or other AEs (medically-attended AEs, SAEs).
  - Record concomitant medications and vaccinations, vaccinations according to instructions in Section 7.6.
  - If the subject reports any concerning local or systemic reactions, or other AEs (e.g., medically-attended AEs, SAEs), these should be followed-up either by a phone call(s) or by an unscheduled site visit based on the judgment of the Investigator.
- Instructions for the subject:
  - Remind the subject to continue recording solicited and unsolicited AEs (i.e., the occurrence of all other AEs) in the eDiary.
  - Remind the subject to call the site immediately to report the following:
    - If he/she experiences any concerning local or systemic reactions or other medical event.
    - Any medically-attended visits that are not routine visits for physical examination or vaccination, such as visits for hospitalization, an emergency room visit, or an otherwise unscheduled visit to or from medical personnel (medical doctor) for any reason.
    - Experience a serious medical event, have a change in overall health or be diagnosed with a new medical condition by a doctor. These should be reported regardless of the perceived relationship between the event and the trial vaccine.
  - Remind the subject to contact the site immediately if he/she has any of the symptoms suggestive of COVID-19. In addition, subjects will be messaged up to twice a week to provide a yes or no response to having COVID-19 symptoms. Those who respond "yes" will be contacted by trial staff for follow-up information, if the investigator considers the symptoms could potentially indicate a COVID-19 case (see Section 9.2.1 and Section 9.5).
  - The subject should also be reminded to contact the site immediately if he/she had a positive SARS-CoV-2 test performed outside of the site, irrespective of whether they were symptomatic (COVID-19 illness) or asymptomatic at the time of the test.

### **9.1.1.3 Clinic Visit 2: Day 29 - Second Trial Vaccination (-3/+7 days)**

#### Pre-vaccination Procedures

- Review and record any newly reported safety data including solicited and unsolicited AEs, or other AEs (medically-attended AEs, SAEs).

- Record concomitant medications and vaccinations, according to instructions in Section 7.6.
- Perform a symptom-directed physical examination (see Section 9.3.6).
- Measure vital signs (body temperature, pulse, blood pressure, see Section 9.3.6).
- Perform urine pregnancy test in females of childbearing potential (Appendix 5).
- Collect pre-vaccination blood samples (see Table 1) for binding antibody testing to RBD of S protein of SARS-CoV-2 (~6 mL blood) and SARS-CoV-2 viral neutralizing activity (~6 mL blood). No testing of antibody to N protein of SARS-CoV-2 will be performed at this time point.
- Collect pre-vaccination blood samples for CMI (~38 mL blood) from subjects of the CMI Subset.

#### Vaccination Procedure

- Review criteria for delay or cancellation of vaccination. See Sections 6.3 and 8.1 for an overview of the criteria leading to delay or cancellation of vaccine administration. In case of delay, the vaccination should take place within the allowed time windows. The reasons for delay or cancellation should be documented in the subject's chart.
- Administer the trial vaccine dose according to the subject's assignment.

#### Post-vaccination Procedures

- Observe the subject on site for at least 30 minutes following vaccination for safety monitoring. At the end of the observation period:
  - Measure vital signs (body temperature, pulse, blood pressure; see Section 9.3.6).
  - The subject may not be discharged until vital signs are within normal range or have returned to pre-vaccination levels.
  - Record the occurrence of any AEs following trial vaccination.
- Instructions for the subject:
  - Re-instruct the subject how to measure solicited AEs and how to complete the eDiary. The subject should record solicited local and systemic AEs occurring on the day of vaccination and the following 7 days, and unsolicited AEs (i.e., the occurrence of all other AEs) occurring on the day of vaccination and the following 28 days.
  - Remind the subject to call the site immediately to report the following:
    - If he/she experiences any concerning local or systemic reactions or other medical event.
    - Any medically-attended visits that are not routine visits for physical examination or vaccination, such as visits for hospitalization, an emergency room visit, or an otherwise unscheduled visit to or from medical personnel (medical doctor) for any reason.

- Experience a serious medical event, have a change in overall health or be diagnosed with a new medical condition by a doctor. These should be reported regardless of the perceived relationship between the event and the trial vaccine.
- Remind the subject to contact the site immediately if he/she has any of the symptoms suggestive of COVID-19. In addition, subjects will be messaged up to twice a week to provide a yes or no response to having COVID-19 symptoms. Those who respond “yes” will be contacted by trial staff for follow-up information, if the investigator considers the symptoms could potentially indicate a COVID-19 case (see Section 9.2.1 and Section 9.5).
- The subject should also be reminded to contact the site immediately if he/she had a positive SARS-CoV-2 test performed outside of the site, irrespective of whether they were symptomatic (COVID-19 illness) or asymptomatic at the time of the test.

#### **9.1.1.4 Phone Call: Day 30 (-0/+0 day)**

The purpose of this phone contact is to inquire about the subject’s general well-being and to assess safety 1 day after the second trial vaccination.

The assessments and procedures are identical to those performed during the phone call on Day 2.

#### **9.1.1.5 Clinic Visit 3: Day 43 (-3/+3 days)**

- Review and record any newly reported safety data including solicited and unsolicited AEs, or other AEs (medically-attended AEs, SAEs).
- Record concomitant medications and vaccinations, according to instructions in Section 7.6.
- Perform a symptom-directed physical examination (see Section 9.3.6).
- Measure vital signs (body temperature, pulse, blood pressure, see Section 9.3.6).
- Collect blood samples (see Table 1) for binding antibody testing to RBD of S protein of SARS-CoV-2 (~6 mL blood); SARS-CoV-2 viral neutralizing activity (~6 mL blood); and binding antibody testing to N protein of SARS-CoV-2 (~6 mL blood).
- Collect blood samples for CMI (~38 mL blood) from subjects of the CMI Subset.
- Instructions for the subject:
  - Inform the subject that recording of solicited local and systemic reactions in the eDiary is complete. Remind the subject to continue recording unsolicited AEs (all AEs).
  - Remind the subject to call the site immediately to report the following:
    - If he/she experiences any concerning medical event.
    - Any medically-attended visits that are not routine visits for physical examination or vaccination, such as visits for hospitalization, an emergency

- room visit, or an otherwise unscheduled visit to or from medical personnel (medical doctor) for any reason.
- Experience a serious medical event, have a change in overall health or be diagnosed with a new medical condition by a doctor. These should be reported, regardless of the perceived relationship between the event and the trial vaccine.
- Remind the subject to contact the site immediately if he/she has any of the symptoms suggestive of COVID-19. In addition, subjects will be messaged up to twice a week to provide a yes or no response to having COVID-19 symptoms. Those who respond “yes” will be contacted by trial staff for follow-up information, if the investigator considers the symptoms could potentially indicate a COVID-19 case (see Section 9.2.1 and Section 9.5).
- The subject should also be reminded to contact the site immediately if he/she had a positive SARS-CoV-2 test performed outside of the site, irrespective of whether they were symptomatic (COVID-19 illness) or asymptomatic at the time of the test.

#### **9.1.1.6 Clinic Visit 4: Day 57 (-3/+7 days)**

- Review and record any newly reported safety data including unsolicited AEs or other AEs (medically-attended AEs, SAEs).
- Record concomitant medications and vaccinations, according to instructions in Section 7.6.
- Perform a symptom-directed physical examination (see Section 9.3.6).
- Measure vital signs (body temperature, pulse, blood pressure, see Section 9.3.6).
- Collect a blood sample for immunogenicity assessment (see Table 1) for binding antibody testing to RBD of S protein of SARS-CoV-2 (~6 mL blood) and SARS-CoV-2 viral neutralizing activity (~6 mL blood). No testing of binding antibody to N protein of SARS-CoV-2 will be performed at this time point.
- Collect blood samples for CMI (~38 mL blood) from subjects of the CMI Subset.
- Instructions for the subject:
  - Inform the subject that reporting of unsolicited AEs is complete.
  - Remind the subject to call the site immediately to report the following:
    - If he/she experiences any concerning medical event.
    - Any medically-attended visits that are not routine visits for physical examination or vaccination, such as visits for hospitalization, an emergency room visit, or an otherwise unscheduled visit to or from medical personnel (medical doctor) for any reason.
    - Experience a serious medical event, have a change in overall health or be diagnosed with a new medical condition by a doctor. These should be reported regardless of the perceived relationship between the event and the trial vaccine.

- Remind the subject to contact the site immediately if he/she has any of the symptoms suggestive of COVID-19. In addition, subjects will be messaged up to twice a week to provide a yes or no response to having COVID-19 symptoms. Those who respond “yes” will be contacted by trial staff for follow-up information, if the investigator considers the symptoms could potentially indicate a COVID-19 case (see Section 9.2.1 and Section 9.5).
- The subject should also be reminded to contact the site immediately if he/she had a positive SARS-CoV-2 test performed outside of the site, irrespective of whether they were symptomatic (COVID-19 illness) or asymptomatic at the time of the test.

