- f. Vital signs will be measured pre- and post-vaccination prior to discharge. Subjects will be observed for at least 30 minutes following each vaccination. Vital signs must be within normal or clinically non-relevant abnormal ranges or have returned to pre-vaccination values for the subject to be discharged.
- g. eDiary (electronic diary) for recording of post-vaccination solicited AEs will be provided to subjects as needed. Subjects should be trained on the use of the eDiary. Solicited local and systemic AEs occurring on the day of vaccination (Day 1 and Day 29) and for the following 7 days will be recorded by the subject in the eDiary. In addition, the eDiary will serve as a memory aid for the subject to report unsolicited AEs occurring on the day of vaccination (Day 1 and Day 29) and for the following 28 days. The data will be reviewed with the subject by trial staff at the site visits on Day 29, Day 43, and Day 57. During phone calls, the subject's general well-being will be checked and the subject should be reminded to complete the safety information by eDiary. If the subject reports by phone any concerning local or systemic reactions, or other AEs (e.g., on Day 2 or Day 30), these should be followed-up either by a phone call(s) or by an unscheduled site visit, based on the judgment of the Investigator.

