### 4.2 Endpoints

#### 4.2.1 Primary Endpoints

##### Primary Safety Endpoints

- Occurrence, intensity and relationship of medically-attended AEs collected through 6 months after the second trial vaccination in all subjects.
- Occurrence, intensity and relationship of SAEs and AESIs collected through 1 year after the second trial vaccination in all subjects.
- Occurrence of fatal SAEs through 1 year after the second trial vaccination in all subjects.
- Occurrence of AEs leading to vaccine withdrawal or trial discontinuation through 1 year after the second trial vaccination in all subjects.
- Occurrence, intensity and duration of each solicited local AE within 7 days after each trial vaccination in a subset of subjects.
- Occurrence, intensity, duration of each solicited systemic AE within 7 days after each trial vaccination in a subset of subjects.
- Occurrence, intensity and relationship of unsolicited AEs occurring within 28 days after each trial vaccination in a subset of subjects.

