#### **9.1.1.7 Clinic Visit 5: Day 120 (-7/+7 days)**

- Review and record any newly reported AEs since the site visit on Day 57 (medically-attended AEs, SAEs).
- Record concomitant medications and vaccinations, according to instructions in Section 7.6.
- Perform a symptom-directed physical examination (see Section 9.3.6).
- Measure vital signs (body temperature, pulse, blood pressure, see Section 9.3.6).
- Collect blood samples (see Table 1) for binding antibody testing to RBD of S protein of SARS-CoV-2 (~6 mL blood) and SARS-CoV-2 viral neutralizing activity (~6 mL blood). No testing of binding antibody to N protein of SARS-CoV-2 will be performed at this time point.
- Collect blood samples for CMI (~38 mL blood) from subjects of the CMI Subset.
- Instructions for the subject:
  - Remind the subject to call the site immediately to report the following:
    - If he/she experiences any concerning medical event.
    - Any medically-attended visits that are not routine visits for physical examination or vaccination, such as visits for hospitalization, an emergency room visit, or an otherwise unscheduled visit to or from medical personnel (medical doctor) for any reason.
    - Experience a serious medical event, have a change in overall health or be diagnosed with a new medical condition by a doctor. These should be reported regardless of the perceived relationship between the event and the trial vaccine.
  - Remind the subject to contact the site immediately if he/she has any of the symptoms suggestive of COVID-19. In addition, subjects will be messaged up to twice a week to provide a yes or no response to having COVID-19 symptoms. Those who respond “yes” will be contacted by trial staff for follow-up information, if the investigator considers the symptoms could potentially indicate a COVID-19 case (see Section 9.2.1 and Section 9.5).

- The subject should also be reminded to contact the site immediately if he/she had a positive SARS-CoV-2 test performed outside of the site, irrespective of whether they were symptomatic (COVID-19 illness) or asymptomatic at the time of the test.

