### 9.3.3.2 Unsolicited Adverse Events and Serious Adverse Events

Unsolicited AEs occurring on the day of vaccination and the following 28 days will be recorded by subjects included in the Immunogenicity/Reactogenicity Subset for each of the 2 trial vaccinations.

For all subjects, medically-attended AEs will be collected through 6 months after the second trial vaccination. AESIs will be collected through 1 year after the second trial vaccination (see Section 9.3.3.3). SAEs will be collected through 1 year after the second trial vaccination.

Medically-attended AEs are defined as AEs with medically-attended visits that are not routine visits for physical examination or vaccination, such as visits for hospitalization, an emergency room visit, or an otherwise unscheduled visit to or from medical personnel (medical doctor) for any reason.

The occurrence of AEs (serious and non-serious) will be assessed by non-directive questioning of the subject at each visit. AEs volunteered by the subject during or between visits as eDiary entries or detected through observation, physical examination, laboratory test, or other assessments during the entire trial, will be recorded in the eCRF if they fulfil the definitions as specified in section 9.3.2. Subjects should be instructed to report immediately any AEs with serious symptoms, subjective complaints or objective changes in their well-being to the Investigator or the site personnel, regardless of the perceived relationship between the event and the trial vaccine.

The Investigator will assess the relationship between trial vaccine and occurrence of each AE/SAE.

Non-serious intercurrent medical conditions that may affect the immune response to vaccination will also be collected throughout the trial.

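### Visit 4 may fall up to 3 days before the 28-day period after dose 2 ends, yet it closes unsolicited-AE reporting regardless of days since dose 2

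*Protocol*

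**What the plan says.** Protocol 4.2.1 lists as a primary safety endpoint: "Occurrence, intensity and relationship of unsolicited AEs occurring within 28 days after each trial vaccination in a subset of subjects". Protocol 9.3.3.2 sets the collection period: "Unsolicited AEs occurring on the day of vaccination and the following 28 days will be recorded by subjects included in the Immunogenicity/Reactogenicity Subset". That is the dose day plus 28 days.

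Protocol Table 1 places Visit 4 at 29+28 with a window of -3/+7 days. Section 9.1.1.6 then directs staff: "Inform the subject that reporting of unsolicited AEs is complete". In Table 1 the row for diary collection of solicited and unsolicited AEs ends at this visit, and footnote g ends staff review of the diary there as well: "The data will be reviewed with the subject by trial staff at the site visits on Day 29, Day 43, and Day 57".

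The next scheduled contact for the subset is Day 120, where Protocol 9.1.1.7 says: "Review and record any newly reported AEs since the site visit on Day 57 (medically-attended AEs, SAEs". Protocol 9.3.3.2 also has a general rule: "The occurrence of AEs (serious and non-serious) will be assessed by non-directive questioning of the subject at each visit".

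SAP 12.6.1.1 tabulates unsolicited AEs within 28 days after each vaccination and after any vaccination, on SAS 2. SAP 12.6.1 bases percentages after the second vaccination on all subjects in the set who received it. Neither section adjusts for days observed.

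**The concern.** The endpoint window is fixed by the dose date, but collection stops at a visit date, and the visit window lets the second come before the first. An ordinary unsolicited AE with onset after an early Visit 4 but within 28 days of dose 2 belongs to the endpoint, yet no scheduled step is designed to capture it. The subject has been told to stop reporting, the diary is no longer reviewed, and the Day 120 checklist names only medically-attended AEs and SAEs.

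The tables would then show a percentage labelled 28 days that rests on a shorter period for some subjects. The error can only go downward, and it sits in a primary safety endpoint. Early visits need not appear in the deviation listings either, because Protocol 9 treats visit windows as guidance in the pandemic setting.

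**Working it through.** **Inputs.** Dose 2 at Day 29; Visit 4 at Day 57, -3/+7 (Protocol Table 1 and 9.1.1.6). Collection covers the dose day and the following 28 days (Protocol 9.3.3.2). Subset on CVnCoV: 840 pooled, 420 per lot (Protocol 10.1.1).

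**The plan's own figures.** Table 5 uses 1 - (1 - p)^n. For p = 0.005 and n = 840: 1 - 0.995^840 = 0.9852, which matches the stated 98.5%. For p = 0.001 and n = 840 the result is 0.5685 (stated 56.8%), and for p = 0.005 and n = 420 it is 0.8782 (stated 87.8%). The zero-event 95% upper bound, 1 - 0.05^(1/840), is 3.56:1000 (stated 3.6:1000).

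**Days lost.**
- Full window after dose 2: 57 - 29 + 1 = 29 calendar days.
- Visit 4 at its earliest: Day 57 - 3 = Day 54, which is 25 days after dose 2.
- Days covered: 54 - 29 + 1 = 26.
- Days without scheduled collection: 29 - 26 = 3, and 3/29 = 10.3%.
- Over both dose windows together: 3/58 = 5.2%.
- Nominal gap to the next scheduled contact: 120 - 54 = 66 days.

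**Effect on detection.** Assume that onsets are spread evenly over the 29 days, that incidence is counted after dose 2, that every event in the gap is lost, and that a share s of subjects is seen on Day 54. The incidence that can be observed is then p × (1 - s × 3/29). The documents do not give s, so a range is shown.

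| s | p = 5:1000, N=840 | p = 1:1000, N=840 | p = 5:1000, N=420 |
|---|---|---|---|
| 0 | 0.9852 | 0.5685 | 0.8782 |
| 0.25 | 0.9835 | 0.5590 | 0.8714 |
| 0.50 | 0.9815 | 0.5493 | 0.8641 |
| 1 | 0.9770 | 0.5293 | 0.8485 |

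With s = 1 and p = 5:1000: 0.005 × 26/29 = 0.00448, and 1 - (1 - 0.00448)^840 = 0.977. The zero-event upper bound for N=840 becomes 3.56 × 29/26 = 3.97:1000.

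These are upper limits on the loss. Onsets that cluster soon after the dose, or events volunteered later, would reduce it. A visit on or after Day 57 loses nothing.

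**The case against.** **Later questioning covers the gap.** This is the strongest reply, and part of it stands. Protocol 9.3.3.2 requires a non-directive question about serious and non-serious AEs at every visit, and Appendix 10 words it as covering the time since the subject was last asked. At Day 120 that reaches back to Visit 4. SAEs, AESIs, medically-attended AEs and AEs leading to withdrawal stay reportable under 9.3.2, and at Visit 4 the subject is reminded to call about any concerning medical event. A reader might infer that the missing days are never asked about; the documents do not support that. What remains is narrower: an ordinary AE must be remembered and volunteered about 66 days later by someone who was told that reporting was complete.

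Whether such an AE would then be entered is unclear. Protocol 9.3.3.2 says AEs volunteered or detected "will be recorded in the eCRF if they fulfil the definitions as specified in section 9.3.2", and 9.3.2 does not list ordinary unsolicited AEs. Read literally, that would bar them at any time, so it cannot be the intended meaning. Protocol 9.3.1 lists them, and SAP 10.5.8 would keep an onset within 28 days of a dose in the tables.

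**The shortfall could be larger.** A reader might count Visit 4 from the first vaccination, since SAP 10.2 defines trial day that way. With dose 2 on Day 36 (29 + 7), a Day 54 visit would be 18 days after dose 2 and would miss 10 of 29 days (34%). The documents point the other way: Table 1 gives 29+28 as the post-vaccination reference, SAP 10.6.1 counts Visit Day 43 from the second vaccination, and Protocol 9.1.1.10 places the Day 393 visit one year after the last dose.

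**The SAP asserts full observation.** A reader might take SAP 10.5.4 this way. It says only which AEs are collected and how they are assigned to a dose. The mismatch lies in the 28-day label and denominator of SAP 12.6.1 and 12.6.1.1.

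**The effect is negligible and the visits are over.** The effect is indeed small, safety analysis is descriptive, and rewording cannot recover past days. The share of subjects affected can still be reported from dates already held.

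**Conclusion.** The point holds as a minor mismatch between a closing instruction and the window of a primary safety endpoint. In subjects whose Visit 4 is early, ordinary unsolicited AEs on up to 3 of the 29 days after dose 2 have no scheduled diary collection or targeted review, and would in practice reach the database only if volunteered later. The after-dose-2 percentages are therefore biased slightly downward. The after-any-dose percentages are affected less, because the dose-1 window is untouched.

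At the extreme of every subject seen 3 days early with even onset, detection at 5:1000 with N=840 moves from 98.5% to 97.7%. The bias should be similar across randomized arms, so the comparison with placebo is barely touched. The size rests on three assumptions: Visit 4 is counted from the actual dose-2 date, onsets are even, and nothing in the gap is volunteered. The real share of early visits is not given.

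**What to change.** Reconcile Protocol 9.1.1.6 and 9.1.1.7 with the endpoint in 4.2.1. Keep unsolicited-AE recording open through 28 days after the actual dose-2 date even when Visit 4 is earlier, and ask at the next contact for any AE with onset up to that date. Alternatively, set the Visit 4 window to -0/+7; the End of Trial visit already uses a window with no early days (-0/+21).

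For data already collected, add one row to the SAP 12.6.1.1 tables giving, by group, the number and percentage of subjects whose Visit 4 took place before 28 days after dose 2. It needs only the dose-2 and Visit 4 dates.

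Cost: a line or two of protocol wording and one table row, with no extra visit. If reporting stays open for the full period, all 29 days are covered and Table 5 stands as printed.
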